2.3 Allocation

As shown in the CONSORT diagrams for Phase I and 2 (Figure 1), 638 potential participants during the Phase 1 study period and 149 during Phase 2 agreed to initial screening for inclusion in the protocol to yield 49 individuals eligible for randomization in Phase 1 and 28 in Phase 2. Participants were randomly allocated to either brief CBT (n=24 in phase 1; n=11 in phase 2) or brief IPT (n=25 in phase 1; n=17 in phase 2) by an independent data manager not otherwise involved in the clinical trial using a permuted block strategy (Matts and Lachin, 1988). The allocation sequence was concealed from all study personnel. Randomization was stratified by gender and depression screening scores, which accounts for imbalances in cell sizes.

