2.4 Outcome Measures

Raters blind to treatment assignment conducted assessments in person (phase 1) or by telephone (phase 2) at baseline, midpoint (week 5), and post-treatment (week 10) except as indicated below. Self-report measures were collected online. Demographic data were recorded on standardized research forms. Psychiatric diagnoses were assigned using Mini-International Neuropsychiatric Interview (MINI version 7.0) (Sheehan et al., 1998). Information about antisocial personality disorder diagnosis was collected using the Structured Clinical Interview for DSM 5—Personality Disorders (SCID-5-PD) (First et al., 2016) Depressive symptoms were assessed using the clinician-rated HRSD-17 (primary outcome measure) and Montgomery Asberg Depression Rating Scale (MADRS) (Montgomery and Asberg, 1979), and the self-report Quick Inventory of Depressive Symptomatology-Self Report (QIDS-SR) (Rush et al., 2003). HRSD-17 scores range from 0 to 52, MADRS scores range from 0 to 60, and QIDS-SR scores range from 0-27, with higher scores indicating greater depression severity on all depression measures. QIDS scores were collected at each therapy visit. Anxiety was rated using the self-reported 7-item Generalized Anxiety Disorder Assessment (GAD-7) (Spitzer et al., 2006) with scores ranging from 0 to 21, with higher scores indicating greater anxiety severity. The self-reported World Health Organization Disability Assessment Schedule 2.0 (WHODAS 2.0), a 36-item measure with higher scores indicating more impairment, was used to assess global functioning (Federici et al., 2017). Acceptability of the intervention was assessed post-treatment with the Client Satisfaction Questionnaire (CSQ) (Attkisson and Greenfield, 1994) which yields scores ranging from 8-32 with higher scores indicating greater levels of satisfaction.

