Both patients and therapists completed brief versions of the Working Alliance Inventory (WAI) (Horvath and Greenberg, 1989) after each therapy session. The therapist (10 items) and patient (12 items) versions of the WAI are designed to yield three alliance scales, corresponding to Bordin's components: Goal, Task, and Bond (Bordin, 1979). Higher scores indicate a more positive rating of working alliance. Both patients and therapists completed the 21-item Strategies in Therapy Use Form (STUF) after each therapy session. The STUF measure, developed for this study, is derived from patient and therapist self-report measures of the Psychotherapy Quality Questionnaire (PQQ) developed by Miranda and colleagues (Hepner et al., 2010; Miranda et al., 2010) to assess psychotherapy use in usual care settings. STUF measures therapeutic strategies used in sessions and is scored to yield IPT, CBT, and non-specific (NS) subscales. Higher scores on the STUF subscales indicate greater use of strategies related to the therapy modality. The CBT, IPT and NS scales showed a high degree of internal reliability across all 8 sessions for both the patient and therapist ratings (Cronbach alphas: .72 - .97; McDonald's Omegas: .70 - .97).

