2.6 Statistical analysis

Analyses were conducted using SPSS28 and HLM8 (SSI, Inc.) statistical software. To compare groups by treatment and phase on baseline demographic and clinical characteristics, and treatment dropout rates and number of sessions completed, Cramer's V and Mann-Whitney Wilcoxon tests were used to compare nominal and ordinal variables, respectively. Independent samples t-tests were used to compare groups by treatment and phase on overall client satisfaction (CSQ). Analyses of outcome and process variables were conducted using hierarchical linear models (HLM, also known as linear mixed effects models) with weekly measures nested within persons (patients) and modeled with random slopes and intercepts, an unstructured variance/covariance matrix, and robust standard errors. HLM allows for inclusion of all subjects with at least baseline data and addresses missing data by using restricted maximum likelihood (REML) estimation. Time was centered at 10 weeks, and variables used for randomization stratification (gender and HRSD-17 screening scores) were included as covariates in all HLM models. Cohen's d-type effect sizes (absolute values) were calculated from model estimates for HLM models and from raw values for simple t-tests.

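### Does section 2.6 leave open which HLM coefficient is the IPT–CBT comparison and hence what d means?

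*Combined protocol and SAP*

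**What the plan says.** Section 2.6 states that "Analyses of outcome and process variables were conducted using hierarchical linear models (HLM, also known as linear mixed effects models", with random intercepts and slopes for patients, an unstructured covariance matrix, robust standard errors and REML. It adds: "Time was centered at 10 weeks, and variables used for randomization stratification (gender and HRSD-17 screening scores) were included as covariates". On effect sizes it says "d-type effect sizes (absolute values) were calculated from model estimates for HLM models and from raw values for simple t-tests".

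Section 2.4 (Outcome Measures) names the "clinician-rated HRSD-17 (primary outcome measure", and gives the rating times as "at baseline, midpoint (week 5), and post-treatment (week 10) except as indicated below". It attaches neither a time point nor a level-or-change definition to the primary outcome. For the process measures it says "Both patients and therapists completed the 21-item Strategies in Therapy Use Form (STUF) after each therapy session"; the WAI follows the same session-by-session schedule.

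Section 2.3 (Allocation) gives the arm sizes: "brief CBT (n=24 in phase 1; n=11 in phase 2) or brief IPT (n=25 in phase 1; n=17 in phase 2".

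No section lists arm, phase or arm-by-time among the HLM terms, designates one coefficient as the comparison of the two therapies, or names the SD used for d.

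**The concern.** With the usual arm, time and arm-by-time terms, a model with time zero at week 10 yields two arm coefficients, each with its own test. The arm term is the difference at week 10; the arm-by-time term is the difference in weekly change. They use the three HRSD-17 ratings differently, so two analysts who each test one of them on the same data could reach different conclusions on the primary outcome. If the choice were made after both p-values were known, the false-positive rate would exceed 5%.

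The issue looks sharper for STUF and WAI. They have no pre-treatment value, so an arm gap present from the first session shows up in the week-10 term and not at all in the arm-by-time term. The unnamed SD adds a second degree of freedom to d, though not to the tests.

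**Working it through.** **Inputs from the documents.** CBT 24 + 11 = 35; IPT 25 + 17 = 42; total 77, which agrees with 49 + 28. HRSD-17 at weeks 0, 5 and 10. Time zero at week 10. The documents give no power calculation, alpha, SD, correlation or expected difference, so there is no figure of the plan's own to reproduce. Two-sided 5% is assumed.

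**What each coefficient estimates.** Take y = b0 + b1(t − 10) + b2·arm + b3·arm·(t − 10). The week-10 difference is b2 and the difference in 10-week change is 10·b3. They differ by b2 − 10·b3, the fitted arm difference at baseline.

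With complete data and before covariates, person-level least squares at times −10, −5 and 0 gives these weights on the observed arm differences:

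| Estimate | Baseline | Week 5 | Week 10 |
|---|---|---|---|
| Week-10 value | −1/6 | 2/6 | 5/6 |
| 10 × slope | −1 | 0 | 1 |

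The two are therefore different quantities. The observed baseline arm difference has SE √(1/35 + 1/42) = 0.229 SD before covariates, so chance alone can put it anywhere within about ±1.96 × 0.229 = ±0.45 SD.

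**What the centring does.** Moving the time origin changes the meaning of b2 and leaves b3, its SE and its test unchanged. An analyst interested only in b3 has no use for centring at week 10. The choice therefore points to b2, the post-treatment difference.

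**How often the tests part company.** All variances here are assumed. The grid has baseline SD 3.5 to 5, week-10 SD 5.5 to 7, residual SD 2 to 3 and baseline/week-10 correlation 0.2 to 0.5, with 89 admissible sets. It takes 35 vs 42 patients, complete data, linear time and equal SDs in both arms. Median SEs are 1.42 (week 10) and 1.41 (change), and the median correlation of the two estimates is 0.84.

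| True week-10 difference (points) | Exactly one test significant: median (range) |
|---|---|
| 0 | 5% (3.5–7.2%) |
| 1 | 9% (5.5–14.6%) |
| 2 | 16% (10–27%) |
| 3 | 19% (13–27%) |
| 4 | 13% (5–21%) |

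A bivariate normal calculation at the median SEs and correlation, with cut-offs ±1.96, gives 5.1%, 8.6%, 15.7%, 18.0% and 12.4%, in line with the grid.

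Under no difference, the chance that at least one test is significant is 7.5% (6.7–8.6%). This fits the first row of the table: both are significant in 5 + 5 − 7.5 = 2.5% of trials, so exactly one is in 7.5 − 2.5 = 5%.

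At the median SEs and correlation, the SD of the gap between the two estimates is √(1.42² + 1.41² − 2 × 0.84 × 1.42 × 1.41) = 0.80 points. Its mean absolute size is 0.80 × √(2/π) = 0.64, against 0.65 on the grid.

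**Covariates.** Read as a main effect, the screening score adjusts only the week-10 term. Letting it act on the slope as well leaves median discordance at 3 points at 18.7% and moves the median SEs by about 0.002. This part of the concern has no practical effect.

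**STUF and d.** A constant 1-SD gap gives d = 1.0 at week 10 and 0 for change; a gap growing from 0 to 1 SD gives 1.0 for both. Both patterns are hypothetical. For the SD choice, a 2-point difference is 2/4 = 0.50 with an assumed baseline SD of 4 and 2/6.5 = 0.31 with an assumed week-10 SD of 6.5. The p-values do not change.

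**The case for a change.** The strongest case for acting is that centring tells the reader what an arm term would mean if it is the comparison, but not that it is the comparison. A random-slope model supports an arm-by-time test equally well, and trials of this kind often report one. The discordance figures hold up under separate calculation. The STUF arithmetic needs no assumed variance, and a reader could be told that the therapies were clearly differentiated or not, depending on an unstated choice. Two or three sentences would settle it at no analytic cost.

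Much of this stands as description: the fixed effects are not listed, the contrast is implied and not named, and the SD for d is missing. It does not show a wrong analysis. The two-coefficient conflict depends on an arm-by-time term that section 2.6 does not list; phase might be in the model too. The 7.5% needs a coefficient to be selected after both tests are seen, and the documents do not show that. A model with arm on intercept and slope produces both coefficients, and an analyst who reports both leaves nothing for readers to disagree about.

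For STUF and WAI, process measures and not the primary outcome, a mean difference over sessions would be one analyst's preference, not the repair of an error. A signed difference with its interval and a named SD are reporting refinements.

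**Conclusion.** The concern does not call for a change. Section 2.6 omits detail, but its centring at week 10 supplies the natural reading of the arm coefficient: the post-treatment difference between the therapies. Either coefficient from the stated model would be a valid comparison, and no stated rule yields a biased estimate or an invalid test.

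The size of the ambiguity is moderate: about 5% discordance with no true difference, up to about 19% at a true 3 points. It rests wholly on assumed variances, complete data, linear time and a model containing both arm terms. The 7.5% figure also needs selection after the results are known.

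Section 2 describes, in the past tense, a study that ended in March 2021. Writing the contrast down now would help a reader interpret d, but it could not restore prespecification. This is a gap that analysts fill sensibly.
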